### 3. Age and Reproductive Status

- a) Males and Females, age 18 or older
- b) Women of childbearing potential (WOCBP) must have a negative serum or urine pregnancy test (minimum sensitivity 25 IU/L or equivalent units of HCG) within 24 hours prior to the start of study drug.
- c) Women must not be breastfeeding.
- d) Males who are sexually active with WOCBP must agree to follow instructions for method(s) of contraception for the duration of study treatment with nivolumab and 7 months after the last dose of study treatment {i.e., 90 days (duration of sperm turnover) plus the time required for the investigational drug to undergo approximately five half-lives.} or 100 days post-treatment completion for subject receiving sorafenib.
- e) Azoospermic males and WOCBP who are continuously not heterosexually active are exempt from contraceptive requirements. However they must still undergo pregnancy testing as described in this section.
- f) Women of childbearing potential (WOCBP) must agree to follow instructions for method(s) of contraception for the duration of study treatment with nivolumab and 5 months after the last dose of study treatment {i.e., 30 days (duration of ovulatory cycle) plus the time required for the investigational drug to undergo approximately five half-lives.} or 40 days post-treatment completion if receiving sorafenib.

Investigators shall counsel WOCBP and male subjects who are sexually active with WOCBP on the importance of pregnancy prevention and the implications of an unexpected pregnancy. Investigators shall advise WOCBP and male subjects who are sexually active with WOCBP on

the use of highly effective methods of contraception. Highly effective methods of contraception have a failure rate of < 1% per year when used consistently and correctly.

At a minimum, subjects must agree to the use of one highly effective method of contraception as listed below:

## **HIGHLY EFFECTIVE METHODS OF CONTRACEPTION**

- Male condoms with spermicide
- Hormonal methods of contraception including combined oral contraceptive pills, vaginal ring, injectables, implants, and intrauterine devices (IUDs) such as Mirena® by WOCBP subject or male subject's WOCBP partner.
- Nonhormonal IUDs, such as ParaGard®
- Tubal ligation
- Vasectomy.
- Complete Abstinence\*

\*Complete abstinence is defined as complete avoidance of heterosexual intercourse and is an acceptable form of contraception for all study drugs. Subjects who choose complete abstinence are not required to use a second method of contraception, but female subjects must continue to have pregnancy tests. Acceptable alternate methods of highly effective contraception must be discussed in the event that the subject chooses to forego complete abstinence.

### **3.3.2.2 *Exclusion Criteria***

#### **1. Target Disease Exceptions**

- a) Known fibrolamellar HCC, sarcomatoid HCC, or mixed cholangiocarcinoma and HCC
- b) Prior liver transplant
- c) History of hepatic encephalopathy
- d) Clinically significant ascites as defined by:
  - i) Any ascites by physical examination at screening or
  - ii) Any prior or current ascites requiring treatment
- e) Evidence of portal hypertension with bleeding esophageal or gastric varices within the past 6 months
- f) Active brain metastases or leptomeningeal metastases. Subjects with treated brain metastases are eligible if the following criteria are fulfilled:
  - i) The brain lesions have been treated and there is no magnetic resonance imaging (MRI) evidence of progression for at least 4 weeks after treatment is complete and

within 28 days prior to the first dose of study drug administration. (If an MRI is contraindicated, a CT scan is acceptable after discussion with the study Medical Monitor.)

- ii) There is no requirement for immunosuppressive doses of corticosteroids (> 10 mg/day prednisone equivalents) for at least 2 weeks prior to study drug administration.
- iii) The case is discussed with the study Medical Monitor

## 2. Medical History and Concurrent Diseases

- a) Infections:
  - i) Active co-infection with
    - (1) Both hepatitis B and C as evidenced by detectable HBV surface antigen or HBV DNA and HCV RNA, OR
    - (2) Hepatitis D infection in subjects with hepatitis B.
  - ii) Subjects with a history of coinfection with both hepatitis B and C, including
    - (1) HBV DNA positive or HBV surface antigen positive subjects with detectable HCV ab, OR
    - (2) HCV RNA positive subjects with resolved HBV infection as evidenced by detectable HBV surface antibody, detectable HBV core antibody, undetectable HBV DNA, and undetectable HBV surface antigen.
  - iii) Known history of testing positive for human immunodeficiency virus (HIV) or known acquired immunodeficiency syndrome (AIDS)
  - iv) Active bacterial or fungal infections requiring systemic treatment within 7 days prior to screening.
- b) Interstitial lung disease that is symptomatic or may interfere with the detection and management of suspected drug-related pulmonary toxicity.
- c) History of active cardiac disease as evidenced by the following:
  - i) Uncontrolled hypertension which defined as systolic blood pressure > 150 mmHg or diastolic blood pressure > 90 mmHg despite optimal medical management
  - ii) Congestive heart failure NYHA (New York Heart Association) class > 2 ([Appendix 6](#))
  - iii) Active coronary artery disease, unstable or newly diagnosed angina or myocardial infarction < 6 months prior to study entry.
  - iv) Cardiac arrhythmias requiring anti-arrhythmic therapy other than beta blockers or digoxin
  - v) Valvular heart disease > CTCAE Grade 2
  - vi) QTc (Fridericia) > 450 msec on two consecutive ECGs (baseline ECG should be repeated if QTc is found to be > 450 msec)

- d) Thrombotic or embolic events (except HCC tumor thrombus) within the past 6 months, such as cerebrovascular accident (including transient ischemic attacks), pulmonary embolism
- e) Any other hemorrhage/bleeding event  $\geq$  CTCAE Grade 3 within 8 weeks except for esophageal or gastric varices (Target disease exception 1.e.)
- f) History of non-healing wounds or ulcers, or bone fractures within 3 months of study entry
- g) Major surgical procedure, open biopsy, or significant traumatic injury within 4 weeks prior to start of investigational product administration or those who receive minor surgical procedures (eg, core biopsy or fine needle aspiration) within 1 week prior to the start of investigational product.
- h) Prior organ allograft or allogeneic bone marrow transplantation
- i) Subjects who are unable to swallow tablets, requiring intravenous alimentation, malabsorption syndrome, or any conditions affecting gastrointestinal absorption; or active peptic ulcer disease.
- j) Pre-existing thyroid abnormality with thyroid function that cannot be maintained in the normal range with medication.
- k) Subjects with any active, known, or suspected autoimmune disease.
  - i) Subjects with vitiligo, type 1 diabetes mellitus, resolved childhood asthma or atopy are permitted to enroll.
  - ii) Subjects with suspected autoimmune thyroid disorders may be enrolled if they are currently euthyroid or with residual hypothyroidism requiring only hormone replacement.
  - iii) Subjects with psoriasis requiring systemic therapy must be excluded from enrollment
- l) Prior malignancy active within the previous 3 years except for locally curable cancers that have been apparently cured, such as basal or squamous cell skin cancer, superficial bladder cancer, or carcinoma in situ of the prostate, cervix, or breast.
- m) Subjects with a condition requiring systemic treatment with either corticosteroids ( $> 10$  mg/day prednisone equivalent) or other immunosuppressive medications within 14 days of study administration. Inhaled or topical steroids and adrenal replacement doses  $> 10$  mg/day prednisone equivalents are permitted in the absence of active autoimmune disease.
- n) Any serious or uncontrolled medical disorder that in the opinion of the investigator may increase the risk associated with study participation or study drug administration, impair the ability of the subject to receive protocol therapy, or interfere with the interpretation of study results.

### 3. Prior and Current Therapies

- a) Prior therapy with an anti-PD-1, anti-PD-L1, anti-PD-L2, anti-CD137, or anti-CTLA-4 antibody (or any other antibody or drug specifically targeting T-cell costimulation or checkpoint pathways)

- b) Prior participation in a BMS nivolumab study.
- c) Prior use of systemic investigational agents for HCC.
- d) Treatment with strong CYP3A4 inducers within 7 days of study entry, including rifampin (and its analogues) or St John's wort.
- e) Current therapeutic anticoagulation therapy.
- f) Treatment with anti-platelet therapy (aspirin at dose  $\geq$  300 mg/day, clopidogrel at dose  $\geq$  75 mg/day)
- g) Radiotherapy within 4 weeks prior to start of study drug. Palliative radiotherapy for symptomatic control is acceptable if completed at least 2 weeks prior to study drug administration) and no additional radiotherapy for the same lesion is planned.

#### **4. Physical and Laboratory Test Findings**

- a) Positive pregnancy test
- b) Baseline serum sodium  $<$  130 mmol/L
- c) Baseline serum potassium  $<$  3.5 mmol/L (potassium supplementation may be given to restore the serum potassium above this level prior to study entry)

#### **5. Allergies and Adverse Drug Reaction**

- a) Known or suspected allergy to nivolumab or sorafenib or study drug components
- b) History of severe hypersensitivity reaction to any monoclonal antibody

#### **6. Sex and Reproductive Status**

- a) WOCBP who are pregnant or breastfeeding
- b) Women with a positive pregnancy test at enrollment or prior to administration of study medication

#### **7. Other Exclusion Criteria**

- a) Prisoners or subjects who are involuntarily incarcerated
- b) Subjects who are compulsorily detained for treatment of either a psychiatric or physical (eg, infectious disease) illness.

### **3.3.3 Nivolumab plus Ipilimumab Combination Cohort**

#### **3.3.3.1 Inclusion Criteria**

##### **1. Signed Written Informed Consent**

- a) Subjects must have signed and dated an IRB/IEC approved written informed consent form in accordance with regulatory and institutional guidelines. This must be obtained before the performance of any protocol related procedures that are not part of normal subject care.
- b) Subjects must be willing and able to comply with scheduled visits, treatment schedule, laboratory testing, and other requirements of the study.

c) Subject Re-enrollment: This study permits the re-enrollment of a subject that has discontinued the study as a pre-treatment failure (ie, subject has not been randomized / has not been treated). If re-enrolled, the subject must be re-consented and inclusion/exclusion criteria reassessed.

## 2. Target Population

- a) Subjects with advanced hepatocellular carcinoma
  - i) Disease not eligible for surgical and/or locoregional therapies
  - ii) Documented radiographic progression during or after sorafenib therapy or sorafenib intolerance as defined in [Section 1.4.9](#).
- b) Histologic confirmation of hepatocellular carcinoma.
  - i) Subjects with only a radiologic diagnosis of HCC may be enrolled for screening in the study but histological confirmation is mandatory prior to the start of study therapy.
  - ii) Evaluable tumor tissue (formalin-fixed, paraffin embedded archival or recent acquisition) must be received by the central vendor (1 block or 15 unstained slides) for correlative studies prior to randomizing a study subject. If archived samples are not available, subjects must consent to a pre-treatment fresh biopsy as a condition of protocol participation. (Note: Fine needle aspiration (FNA) and bone metastases samples are not acceptable for submission).
- c) At least one RECIST 1.1 measurable untreated lesion. All subjects must have at least one previously untreated, unidimensionally measurable lesion by contrast-enhanced spiral computed tomography (CT)  $\geq 10$  mm or contrast enhanced dynamic magnetic resonance imaging (MRI) scan  $\geq 10$  mm (malignant lymph nodes must be  $\geq 15$  mm on short axis).
  - i) The lesion can be accurately measured uni-dimensionally according to RECIST 1.1 criteria
  - ii) The lesion has not been previously treated with surgery, radiotherapy, and/or locoregional therapy (eg: radiofrequency ablation [RFA], percutaneous ethanol [PEI] or acetic acid injection [PAI], cryoablation, high-intensity focused ultrasound [HIFU], transarterial chemoembolization [TACE], transarterial embolization [TAI], etc.)
- d) Locoregional therapy for HCC must be completed at least 4 weeks prior to the baseline scan. All acute toxic effects of any prior local treatment must have resolved to National Cancer Institute (NCI) Common Terminology Criteria for Adverse Events (CTCAE) version 4.03 Grade  $\leq 1$ .
- e) Cirrhotic status of Child-Pugh Class A (A5 or A6) ([Appendix 3](#))
- f) Eastern Cooperative Oncology Group (ECOG) Performance Status of 0 to 1 ([Appendix 4](#))
- g) Subjects are eligible to enroll if they have non-viral-HCC or if they have HBV-, or HCV-HCC, defined as follows:

- i) Chronic HBV infection as evidenced by detectable HBV surface antigen or HBV DNA. Subjects with chronic HBV infection must be on antiviral therapy and have HBV DNA < 100 IU/mL.
- ii) Active or resolved HCV infection as evidenced by detectable HCV RNA or antibody.
- h) Screening laboratory values must meet the following criteria, without continuous supportive treatment such as growth factor administration, blood transfusion, coagulation factors and/or platelet transfusion, or albumin transfusion, and should be obtained within 14 days prior to randomization
  - i) Adequate hematologic function:
    - (1) WBC  $\geq$  2000/ $\mu$ L
    - (2) Neutrophils  $\geq$  1500/ $\mu$ L
    - (3) Platelets  $\geq$  60  $\times$  10^3/ $\mu$ L
    - (4) Hemoglobin  $\geq$  8.5 g/dL
  - ii) Prothrombin time (PT)-international normalized ratio (INR)  $\leq$  2.3 or Prothrombin time (PT)  $\leq$  6 seconds above control.
  - iii) Adequate hepatic function with serum albumin  $\geq$  2.8 g/dL, total bilirubin < 3 mg/dL, and AST and ALT  $\leq$  5 times the institutional upper limits of normal Adequate renal function with a creatinine clearance  $>$  40 mL/min (Cockcroft-Gault formula)

### 3. Age and Reproductive Status

- a) Males and Females, age 18 or older
- b) Women of childbearing potential (WOCBP) must have a negative serum or urine pregnancy test (minimum sensitivity 25 IU/L or equivalent units of HCG) within 24 hours prior to the start of study drug.
- c) Women must not be breastfeeding.
- d) Males who are sexually active with WOCBP must agree to follow instructions for method(s) of contraception for the duration of study treatment with nivolumab and 7 months after the last dose of study treatment {i.e., 90 days (duration of sperm turnover) plus the time required for the investigational drug to undergo approximately five half-lives.}.
- e) Azoospermic males and WOCBP who are continuously not heterosexually active are exempt from contraceptive requirements. However they must still undergo pregnancy testing as described in this section.
- f) Women of childbearing potential (WOCBP) must agree to follow instructions for method(s) of contraception for the duration of study treatment with study drug and 5 months after the last dose of study treatment {i.e., 30 days (duration of ovulatory cycle) plus the time required for the investigational drug to undergo approximately five half-lives.}.

Investigators shall counsel WOCBP and male subjects who are sexually active with WOCBP on the importance of pregnancy prevention and the implications of an unexpected pregnancy

Investigators shall advise WOCBP and male subjects who are sexually active with WOCBP on the use of highly effective methods of contraception. Highly effective methods of contraception have a failure rate of < 1% per year when used consistently and correctly.

At a minimum, subjects must agree to the use of one highly effective method of contraception as listed below:

## **HIGHLY EFFECTIVE METHODS OF CONTRACEPTION**

- Male condoms with spermicide
- Hormonal methods of contraception including combined oral contraceptive pills, vaginal ring, injectables, implants, and intrauterine devices (IUDs) such as Mirena® by WOCBP subject or male subject's WOCBP partner.
- Nonhormonal IUDs, such as ParaGard®
- Tubal ligation
- Vasectomy.
- Complete Abstinence\*

\*Complete abstinence is defined as complete avoidance of heterosexual intercourse and is an acceptable form of contraception for all study drugs. Subjects who choose complete abstinence are not required to use a second method of contraception, but female subjects must continue to have pregnancy tests. Acceptable alternate methods of highly effective contraception must be discussed in the event that the subject chooses to forego complete abstinence.

### **3.3.3.2 *Exclusion Criteria***

#### **1. Target Disease Exceptions**

- a) Known fibrolamellar HCC, sarcomatoid HCC, or mixed cholangiocarcinoma and HCC
- b) Prior liver transplant
- c) No history of hepatic encephalopathy
- d) Any prior (within 1 year) or current clinically significant ascites as measured by physical examination and that requires active paracentesis for control
- e) Evidence of portal hypertension with bleeding esophageal or gastric varices within the past 3 months
- f) Active brain metastases or leptomeningeal metastases. Subjects with treated brain metastases are eligible if the following criteria are fulfilled:
  - i) The brain lesions have been treated and there is no magnetic resonance imaging (MRI) evidence of progression for at least 4 weeks after treatment is complete and within 28 days prior to the first dose of study drug administration. (If an MRI is

contraindicated, a CT scan is acceptable after discussion with the study Medical Monitor.)

- ii) There is no requirement for immunosuppressive doses of corticosteroids (> 10 mg/day prednisone equivalents) for at least 2 weeks prior to study drug administration.
- iii) The case is discussed with the study Medical Monitor

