### **3.3 Study Population**

For entry into the study, the following criteria MUST be met. Eligibility criteria for this study have been carefully considered to ensure the safety of the study subjects and to ensure that the results of the study can be used. It is imperative that subjects fully meet all eligibility criteria. No exceptions will be granted.

For entry into the study, the following criteria MUST be met.

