#### **2. Medical History and Concurrent Diseases**

- a) Any history of hepatic encephalopathy
- b) Any prior (within 1 year) or current clinically significant ascites as measured by physical examination and that requires active paracentesis for control
- c) Active coinfection with both hepatitis B and C
- d) Hepatitis D infection in subjects with hepatitis B
- e) Prior malignancy active within the previous 3 years except for locally curable cancers that have been apparently cured, such as basal or squamous cell skin cancer, prostate cancer without evidence of PSA progression or carcinoma in situ such as the following: gastric, prostate, cervix, colon, melanoma, or breast for example.
- f) Subjects with any active autoimmune disease or history of known or suspected autoimmune disease except for subjects with vitiligo, resolved childhood asthma/atopy, type I diabetes mellitus, residual hypothyroidism due to autoimmune condition only requiring hormone replacement, psoriasis not requiring systemic treatment, or conditions not expected to recur in the absence of an external trigger are permitted to enroll.
- g) Uncontrolled or clinically significant cardiac disease
- h) Positive test for human immunodeficiency virus (HIV) or known acquired immunodeficiency syndrome (AIDS)
- i) Known active drug or alcohol abuse
- j) Prior therapy with an anti-PD-1, anti-PD-L1, anti-PD-L2, anti-CD137, or anti-CTLA-4 antibody (or any other antibody or drug specifically targeting T-cell costimulation or checkpoint pathways)
- k) Prior organ allograft or allogeneic bone marrow transplantation
- l) All toxicities attributed to prior anti-cancer therapy other than neuropathy, alopecia and fatigue must have resolved to Grade 1 (NCI CTCAE version 4) or baseline before administration of study drug. Subjects with toxicities attributed to prior anti-cancer therapy which are not expected to resolve and result in long lasting sequelae are permitted to enroll. Neuropathy must have resolved to Grade 2 (NCI CTCAE version 4).
- m) Active bacterial or fungal infections requiring systemic treatment within 7 days
- n) Use of other investigational drugs (drugs not marketed for any indication) within 28 days or at least 5 half-lives (whichever is longer) before study drug administration

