### **7. Other Exclusion Criteria**

- a) Prisoners or subjects who are involuntarily incarcerated
- b) Subjects who are compulsorily detained for treatment of either a psychiatric or physical (eg, infectious disease) illness

Eligibility criteria in this study have been carefully considered to ensure the safety of the study subjects and that the results of the study can be used. It is imperative that subjects fully meet all eligibility criteria.

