## 5 STUDY ASSESSMENTS AND PROCEDURES

### 5.1 Flow Chart/Time and Events Schedule

Table 5.1-1: CA209040 Screening Procedural Outline for Subjects in Dose Escalation and Expansion Phase (Study Days -28 to -1)		
Procedure	Screening Visit	Notes
Eligibility Assessments		
Informed Consent	X	A subject is considered enrolled only when a protocol specific informed consent is signed. Contact IVRS to obtain study subject number.
Inclusion/Exclusion Criteria	X	All inclusion/exclusion criteria should be assessed at screening and confirmed prior to randomization
Disease Status		
Medical History	X	Include any toxicities or allergy related to previous treatments, smoking history, asthma, COPD, Child-Pugh score determination (only Child Pugh scores of 7 points or less are allowed for subjects in the Escalation Phase , and Child Pugh scores of 6 points or less are allowed for subjects in the Expansion Phase ), no history of hepatic encephalopathy. Includes detailed medical history of potential risk factors for potential events such as pulmonary related events.
Archived Tumor tissue block or Unstained slides	X	A fresh tumor biopsy is required at baseline if there is no other record of histological diagnosis of tumor. Tumor material (archived tumor paraffin block or fresh biopsy with a minimum of 15 unstained slides) must be available for correlative studies. If archived material is unavailable, then tumor material from a fresh biopsy must be provided. Biopsied lesions must be distinct from index lesions.
Disease Assessments - Tumor Imaging (CT or MRI of Chest/Abdomen/Pelvis [including triphasic CT of abdomen]; Bone scan if clinically indicated. Brain MRI if history of brain metastasis.	X	
 
• CT or MRI of the chest, abdomen and pelvis with IV contrast, including required tri-phasic evaluation of the liver.
 
• MRI is acceptable if CT is contraindicated.
 
• Modality (CT or MRI) used at baseline should be used across all imaging time points.
 
• Bone scan is required if clinically indicated.
 
• Brain MRI within 28 days prior to first dose of study therapy for subjects with a history of brain metastasis.
 

Disease Assessments - Serum	X	Serum alpha fetoprotein

**Table 5.1-1: CA209040 Screening Procedural Outline for Subjects in Dose Escalation and Expansion Phase (Study Days -28 to -1)**

Procedure	Screening Visit	Notes

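### Combination cohort exclusion 1.c on hepatic encephalopathy is worded backwards; deleting one word corrects it

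*Combined protocol and SAP*

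**What the plan says.** The protocol has three eligibility sections, and each names past hepatic encephalopathy in its exclusion list.

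- Section 3.3.1.2 (Dose Escalation and Expansion Phase), item 2.a: "Any history of hepatic encephalopathy".
- Section 3.3.2.2 (1L Nivolumab vs Sorafenib Cohort), item 1.c: "History of hepatic encephalopathy".
- Section 3.3.3.2 (Nivolumab plus Ipilimumab Combination Cohort), item 1.c: "No history of hepatic encephalopathy".

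Table 5.1-1, the screening schedule for escalation and expansion, states the rule as a condition of entry in its Medical History row: "no history of hepatic encephalopathy. Includes detailed medical history of potential risk factors".

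Section 3.3 says of the eligibility criteria: "No exceptions will be granted". The combination cohort's own criteria close with "It is imperative that subjects fully meet all eligibility criteria".

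**The concern.** An item in an exclusion list names a condition that keeps a subject out. Item 1.c of Section 3.3.3.2 instead names the condition a subject should meet to come in. Applied literally, it turns away everyone without prior encephalopathy and leaves those with it eligible on this point.

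The protocol treats encephalopathy as a serious hepatic sign. It is the example given for drug-related hepatic decompensation in the dose-limiting toxicity definition (Section 3.1.3.1), and encephalopathy of Grade 3 or higher is listed among the examples of clinical deterioration (Section 3.1.7). Section 3.1 says the combination had not been studied before in advanced HCC. At stake are a safety screen in the cohort with the least prior experience, and a sound basis for judging whether a given enrolment complied with the protocol.

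**Working it through.** No arithmetic is involved beyond counting. The check compares the texts.

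**1. Direction of each statement**

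| Place | Role of the item | Effect as worded |
|---|---|---|
| 3.3.1.2, item 2.a | Exclusion | Bars subjects with a history |
| 3.3.2.2, item 1.c | Exclusion | Bars subjects with a history |
| 3.3.3.2, item 1.c | Exclusion | Bars subjects without a history |
| Table 5.1-1, Medical History | Entry condition | Requires no history |
| Table 5.1-2 (1L cohort) | Screening table | Encephalopathy not mentioned |
| Table 5.1-3 (combination cohort) | Screening table | Cut off in the text available; not checkable |

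Of the three exclusion lists, two have the right direction and one is reversed.

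**2. Is a different rule intended for this cohort?** The first group of exclusions in the 1L and combination lists follows the same order: histological subtype, liver transplant, encephalopathy, ascites, varices, brain metastases. Only the encephalopathy item changes direction. Nothing in the available text gives a reason to treat the combination cohort differently.

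**3. Is there a reading that rescues the wording?** Items 1.f.i and 1.f.ii of the same list also use negative phrasing, but they sit under a lead-in saying when subjects with treated brain metastases are eligible, so the negatives are correct there. Item 1.c is top-level and has no such lead-in.

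**4. Is the rule stated correctly elsewhere for this cohort?** In Sections 3.3.3.1 and 3.3.3.2 encephalopathy appears once, in item 1.c. Table 5.1-3 and Appendix 3 (Child-Pugh score) could not be checked.

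**5. What still limits entry?**

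- Inclusion 2.e restricts cirrhotic status to Child-Pugh A5 or A6.
- Exclusion 1.d begins "Any prior (within 1 year) or current clinically significant ascites as measured by physical examination", and applies where paracentesis is needed for control.
- Exclusion 1.e covers variceal bleeding in the past 3 months.
- Inclusion 2.h sets laboratory limits.
- Exclusion 2.h lets the investigator exclude for a serious or uncontrolled disorder.

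These restrict entry of subjects with current decompensation. None expressly excludes a past episode that has resolved.

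**6. Does the correction work?** Without 'No', item 1.c has the same wording as item 1.c of Section 3.3.2.2 and the same sense as item 2.a of Section 3.3.1.2.

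**The case against.** The strongest reply is that this is an editorial slip with only one workable meaning. A site could not run a Child-Pugh A cohort while excluding everyone who had never had encephalopathy, so it would read the item as intended. Entry-style phrasing also appears elsewhere in the exclusion lists: item 2.l of Section 3.3.1.2 says earlier toxicities must have resolved, and item 3.c of Section 3.3.3.2 ends by saying that no further radiotherapy to the same lesion is planned. That pattern suggests a drafting habit and makes it less likely that anyone acted on the reversed sense.

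This stands as a reason to rate the practical effect as small. It does not make the text right, because a safety criterion should not depend on readers setting its wording aside.

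Three further points are fair:

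- The melanoma safety data in Section 1.4.4 (drug-related hepatic select events in 29.0% of 407 subjects, mostly Grade 3-4, at Arm A's combination doses) show that hepatic toxicity matters with this regimen. They are not linked to prior encephalopathy and cannot size this problem.
- Table 5.1-3 may restate the rule correctly, so its absence is established only for the eligibility text.
- A look-back for subjects enrolled with a positive history goes beyond correcting the text, since nothing in the documents shows a conduct problem.

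**Conclusion.** The concern holds. Item 1.c of Section 3.3.3.2 says the reverse of what the protocol requires elsewhere, and it should be corrected because it is an operative safety criterion under a no-exceptions rule. The extent is one criterion in one cohort, which is planned for up to 120 subjects.

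The documents do not give the frequency of prior encephalopathy or show that any subject was affected, so no number can be put on the consequence. That the effect is likely small is a judgement. It assumes that sites read the intent from the neighbouring items and that the other hepatic criteria were applied. That the inversion came from carrying an entry-condition phrase into an exclusion list is likely, but the documents do not say so.

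**What to change.** Delete 'No' from item 1.c of Section 3.3.3.2, so that it matches item 1.c of Section 3.3.2.2. Check Table 5.1-3, the case report form and the enrolment checklist for the same inversion.

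The cost is one word in an administrative letter or the next amendment, plus that check. As a separate and optional step, the sponsor could identify any combination-cohort subject enrolled with a positive history. This adds some work, and the text correction does not depend on it.
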